**9.2.2. TTI-621 Re-Treatment Guidelines (Initiation of New Cycles of Treatment)**

The parameters described in [Table 9](#) should be met for initiation of a new cycle of treatment with TTI-621. Guidelines for intra-cycle dosing, dosing delays and dosing modifications in response to specific treatment-emergent adverse events are provided in Tables 12, 13, 14, 15, 21, 22 and 23.

**Table 9. Requirements for Initiation of a New Cycle with TTI-621**

Parameter	Criterion
ANC	$\geq 1.0 \times 10^9/L$
Platelet Count	$\geq 75 \times 10^9/L$
Bilirubin	$\leq 1.5 \times ULN$
AST, ALT	$\leq 3 \times ULN$ ( $< 5 \times ULN$ if liver metastases)
Treatment-Related Adverse Event	NCI CTCAE Grade $< 2$ or baseline level (except for alopecia)

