**Table 16. Requirements for Re-Treatment with Doxorubicin on Day 1 (Cycle 2 through Cycle 6)**

Parameter	Criterion
Platelets	$\geq 75 \times 10^9/L$
ANC	$\geq 1 \times 10^9/L$
Organ toxicity or other treatment-related adverse event	Grade $\leq 2$
Bilirubin	$\leq 1.5 \times ULN$
AST, ALT	$\leq 3 \times ULN$ ( $< 5 \times ULN$ if liver metastases)

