Any platelet count with clinically-relevant bleeding (more than easily-controlled epistaxis, mild gum bleeding or menses)	
 
• Hold TTI-621 on Day 8
 
• Monitor platelet recovery (CBC twice weekly recommended)
 
• Consider platelet transfusion per ASCO guidelines
 
• On Day 1 of next cycle: 
 
◦ if platelets have recovered to <math>\geq 75 \times 10^9/L</math> and bleeding has resolved, reduce doxorubicin and TTI-621 by one dose level and initiate cycle
 
◦ if platelets have not recovered to <math>\geq 75 \times 10^9/L</math> and/or bleeding has not resolved, hold doxorubicin and TTI-621 and monitor platelets; initiate the cycle when platelets recover to <math>\geq 75 \times 10^9/L</math> with doxorubicin and TTI-621 each at one dose level reduction
 
 
 
• In the case of a second occurrence of platelet count decreased with bleeding attributed to study drug treatment, consult with the sponsor medical monitor regarding management
 
• The reduced dose levels of doxorubicin and TTI-621 should be used for the remaining combination cycles
 
• When the subject completes the combination portion of the study and moves to TTI-621 monotherapy: 
 
◦ the original TTI-621 should be re-instated and platelet counts monitored
 
◦ in the case of platelets <math>< 50 \times 10^9/L</math> on D15, hold TTI-621 until platelets are <math>\geq 50 \times 10^9/L</math> and then continue with TTI-621 at one dose level reduction
 
◦ on Day 1 of the next cycle, if platelet count remains <math>\geq 50 \times 10^9/L</math>, the reduced TTI-621 dose level should be used for the remainder of the subject's participation. If platelet counts do not remain <math>\geq 50 \times 10^9/L</math>, reduce TTI-621 by another dose level and monitor for tolerability.
 
◦ in the absence of disease progression, further dose reductions may be implemented after discussion with the Sponsor Medical Monitor.
 
 
 

**Table 23. TTI-621 Treatment Guidelines based on Thrombocytopenia Assessed as Related to Study Treatment in Cycles  $\geq 7$  (TTI-621 Monotherapy)**

Note that these guidelines are intended to address a patient who has not experienced thrombocytopenia in the combination portion of the study but presents with thrombocytopenia during monotherapy treatment.

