Day 15 Platelet Count	Management Guidelines
$<\text{LLN} - 75 \times 10^9/\text{L}$	
 
Continue TTI-621 at same dose
 

$<75 \times 10^9 - 50 \times 10^9/\text{L}$	
 
Continue TTI-621 at same dose
 

$<50 \times 10^9 - 25 \times 10^9/\text{L}$ OR Any platelet count with bleeding attributed to study drug treatment	
 
Monitor platelet recovery (CBC twice weekly recommended)
 
Consider platelet transfusion per ASCO guidelines if clinically indicated
 
Hold TTI-621 until platelets are <math>\geq 50 \times 10^9/\text{L}</math> and then continue with TTI-621 at a one dose level reduction
 
On second occurrence of platelets <math>< 50 \times 10^9/\text{L}</math> without other causality, reduce TTI-621 by an additional dose level and monitor for tolerability; in the absence of disease progression, further dose reductions may be implemented after discussion with the Sponsor Medical Monitor
 

$<25 \times 10^9/\text{L}$	
 
Monitor platelet recovery (CBC twice weekly recommended)
 
Consider platelet transfusion per ASCO guidelines if clinically indicated
 
Hold TTI-621 until platelets are <math>\geq 50 \times 10^9/\text{L}</math> and then continue with TTI-621 at a one dose level reduction.
 
On second occurrence of platelets <math>< 25 \times 10^9/\text{L}</math> without other causality, reduce TTI-621 by an additional dose level and monitor for tolerability or consult with the Sponsor Medical Monitor regarding management. In the absence of disease progression, further dose reductions may be implemented after discussion with the Sponsor Medical Monitor.
 

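### Table 9 and the bleeding row of Table 22 give different Day 1 platelet instructions for TTI-621 monotherapy, and nothing says which governs

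*Protocol*

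**What the plan says.** Protocol Section 9.2.2 states that the Table 9 parameters "should be met for initiation of a new cycle of treatment with TTI-621". The platelet criterion in Table 9, headed "Requirements for Initiation of a New Cycle with TTI-621", is at least 75 × 10^9/L. It carries no cycle limit and no separate monotherapy value, whereas the parallel doxorubicin table (Table 16) is limited by its title to Cycles 2 to 6. Section 9.2.2 then refers the reader to other tables, including 22 and 23, for "Guidelines for intra-cycle dosing, dosing delays and dosing modifications in response to specific treatment-emergent adverse events".

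Sections 5.1, 5.2.2 and 5.2.3 apply Section 9.2.2 to patients who stop doxorubicin early and move to TTI-621 alone. They may do so only if the re-treatment guidelines in that section are met.

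Table 22 (Section 9.5) has a row headed "Any platelet count with clinically-relevant bleeding". Its bullets for a patient who has moved to monotherapy include a rule that begins "on Day 1 of the next cycle, if platelet count remains" at or above 50 × 10^9/L. In that case the reduced TTI-621 level is kept for the rest of participation. If the count does not stay there, the instruction is to "reduce TTI-621 by another dose level and monitor for tolerability".

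Table 23 covers patients whose first thrombocytopenia arises on monotherapy. It is keyed to the Day 15 count. Its lower rows say "Hold TTI-621 until platelets are" at least 50 × 10^9/L, then continue one level lower.

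**The concern.** Day 1 of the next cycle is the start of a new cycle, which is what Table 9 regulates. One table asks for 75 × 10^9/L at that point. The other gives an instruction keyed to 50 and states no hold below it. A site with a monotherapy patient at, say, 60 × 10^9/L on Day 1 can cite the protocol either for waiting or for continuing at the reduced level.

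Thrombocytopenia is listed as an adverse event of special interest (Protocol 13.5.8) and is the main Grade 3 or higher treatment-related event described for TTI-621 (Protocol 3.4, 3.7.1). Treatment delays are part of the safety endpoints (Protocol 4.2, 4.4), and the SAP (Section 9.1) summarises held infusions, dose reductions and cycle delays. The same count could be recorded as a cycle delay at one site and as a dose or a reduction at another. The patients directly concerned are those who have already had clinically relevant bleeding.

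**Working it through.** No formula applies. The check sets the platelet thresholds side by side for Day 1 of a monotherapy cycle, in a patient managed under the bleeding row of Table 22.

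| Day 1 count (× 10^9/L) | Table 9 platelet criterion | Table 22, bleeding row, monotherapy | Same instruction? |
|---|---|---|---|
| 75 or more | met | keep the reduced level | yes |
| 50 to below 75 | not met | keep the reduced level; no hold stated | no |
| below 50 | not met | one further level down and monitor; no hold stated | no |

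Three further comparisons bear on how to read this.

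1. *Combination bullets of the same row.* On Day 1 of the next combination cycle, the cycle starts at reduced doses if platelets have recovered to 75 and bleeding has resolved. Otherwise both drugs are held until 75. This agrees with Table 9. The row therefore writes out the hold where one is meant in combination, and omits it in monotherapy.

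2. *Other rows of Table 22 (25 to 50, and below 25).* Their monotherapy bullets hold a Day 15 dose until the count is at least 50, then reduce by one level, with a further reduction on a second count below 50. None names Day 1 of a monotherapy cycle. They meet Table 9 only if the Day 15 hold runs into the next Day 1, or if the second low count falls on a Day 1.

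3. *Table 23.* Its rows are headed by the Day 15 count and it has no Day 1 instruction. It meets Table 9 in the same indirect way.

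The direct conflict is thus confined to one row. It also comes late in a sequence: clinically relevant bleeding during combination, then monotherapy, then (as the bullets are ordered) a Day 15 count below 50 with a hold and a one-level reduction, and then a Day 1 count below 75.

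**The case against.** Two readings would remove the conflict. Under the first, Table 9 decides whether the cycle may start and the Table 22 bullet only sets the level for when it does. Its wording does concern the dose level and does not expressly authorise an infusion that day. Under the second, the specific guidance overrides the general. The note to Table 13 and Section 9.5 make Tables 22 and 23 the dedicated thrombocytopenia guidance, and the reference in Section 9.2.2 to delays and modifications need not be confined to events within a cycle.

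Each reading is plausible. They give opposite answers at a Day 1 count of 50 to below 75, and no sentence chooses between them. The first also has to explain why the combination bullets of the same row state the hold to 75 and the monotherapy bullets do not. What stands is that this is an unresolved ambiguity between stated rules, not proof that sites were told to dose below the Table 9 minimum.

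A reader might infer three stronger things, and the documents support none of them:

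- *That about 14 patients are affected*, from the 22% to 24% Grade 3 or higher thrombocytopenia in the earlier study (0.22 × 62 = 13.6; 0.24 × 62 = 14.9). Those rates count events at any time under weekly dosing in another study, not Day 1 counts in monotherapy. Protocol 3.7.1 describes the falls as resolved by the next weekly infusion, and 3.8.1 reports no increased bleeding risk. The number of patients reaching monotherapy is not given.
- *That the closure of Cohort B illustrates this conflict.* SAP 4.3.2 attributes the closure to Day 8 counts during combination therapy, where the Day 1 rules agree with Table 9.
- *That Table 23 contradicts Table 9 outright.* It gives no Day 1 rule.

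**Conclusion.** The point holds for the monotherapy bullets of Table 22's bleeding row: at Day 1 counts below 75 × 10^9/L the protocol gives two different instructions and does not say which governs. Elsewhere in Tables 22 and 23 the conflict arises only if a Day 15 hold or a second low count reaches the next Day 1.

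The number of patients affected cannot be estimated from the documents and is probably small. The effect is on consistent handling of an adverse event of special interest and on descriptive summaries of reductions and delays. No effect on the objective response rate, the Simon decision or DLT evaluation is shown. The conclusion assumes that no site communication outside the two documents has already settled the matter. The SAP cites one such letter (PACL No 5), on the enrolment change in Cohort B, so others may exist. It is worth correcting because it concerns a safety rule and the correction is cheap.

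**What to change.** Reconcile Section 9.2.2 and Table 9 with the monotherapy bullets of Table 22 and with Table 23. The clarification should state:

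- which passage governs Day 1 of monotherapy cycles, including monotherapy that starts early under Sections 5.1, 5.2.2 and 5.2.3;
- whether the Day 1 bullet in the bleeding row sets only the dose level or also permits dosing on that day, both at or above 50 × 10^9/L and below it;
- what applies when a Day 15 hold, or a second low count, reaches the next Day 1.

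Which threshold is right is for the sponsor's clinical team, and this review takes no position on it. The cost is a protocol clarification letter. It needs no new data and no change to the planned analyses.

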**9.2.3. TTI-621 Dose Modification Guidelines**

The expansion portion of the study is intended to evaluate two dose levels of TTI-621. The lower dose level will be 0.2 mg/kg but the higher dose level is not yet known. Therefore, [Table 10](#) describes modifications for a range of target starting dose levels (Dose Level 1). Provision is not made for treatment with TTI-621 at a dose level below 0.2 mg/kg, but a lower dose level may be allowed after consultation with the Sponsor Medical Monitor for a patient who is receiving clinical benefit and remaining on treatment is, in the opinion of the Investigator, a reasonable treatment option for the patient.

**Table 10. TTI-621 Dose Modifications**

Dose Level	Dose Level -1	Dose Level -2
2.0 mg/kg	1.4 mg/kg	1.0 mg/kg
1.4 mg/kg	1.0 mg/kg	0.7 mg/kg
1.0 mg/kg	0.7 mg/kg	0.5 mg/kg
0.7 mg/kg	0.5 mg/kg	0.2 mg/kg
0.5 mg/kg	0.2 mg/kg	Discontinue
0.2 mg/kg	Discontinue	Discontinue

### 9.2.3.1. Infusion-Related Reactions Related to TTI-621 Administration

Infusion-related reactions will be graded as described in [Table 11](#).

**Table 11. Definition of Infusion-Related Reaction by CTCAE Grade**

CTCAE Grade	Definition
Grade 1 IRR	Mild transient reaction; infusion interruption not indicated; intervention not indicated
Grade 2 IRR	Therapy or infusion interruption indicated but responds promptly to symptomatic treatment (e.g., anti-histamines, NSAIDS, narcotics, IV fluids); prophylactic medications indicated for $\leq$ 24 hours
Grade 3 IRR	Prolonged (i.e., not rapidly responsive to symptomatic medication, brief interruption of infusion, or both); recurrence of symptoms following initial improvement; hospitalization indicated for clinical sequelae
Grade 4 IRR	Life-threatening consequences; urgent intervention indicated

Note: An acute infusion reaction may occur with an agent that causes cytokine release (e.g., monoclonal antibodies or other biological agents). Signs and symptoms usually develop during or shortly after drug infusion and generally resolve completely within 24 hours of completion of infusion. Signs/symptoms may include: allergic reaction/hypersensitivity (including drug fever); arthralgia (joint pain); bronchospasm; cough; dizziness; dyspnea (shortness of breath); fatigue (asthenia, lethargy, malaise); headache; hypertension; hypotension; myalgia (muscle pain); nausea; pruritis/itching; rash/desquamation; rigors/chills; sweating (diaphoresis); tachycardia; tumor pain (onset or exacerbation of tumor pain due to treatment); urticaria (hives, welts, wheals); vomiting.

As described in [Section 5.2.1](#), prophylaxis is required prior to infusion of TTI-621. Patients will be closely monitored for signs and symptoms of hypersensitivity or allergic reactions. Guidelines for management of infusion-related reactions are presented in [Table 12](#).

**Table 12. Management of Infusion-Related Reactions Associated with TTI-621 Administration**

CTCAE Grade	Management Guidelines
Grade 1 Infusion-Related Reaction	
 
The infusion may be stopped or continued at a reduced (50%) infusion rate at the discretion of the Investigator.
 
If symptoms resolve, the infusion can be re-started or increased, as tolerated, to the baseline rate.
 
The patient may receive appropriate further treatment for infusion-related reaction if clinically indicated per the site's standard practice for management of IRR.
 

Grade 2 Infusion-Related Reaction	
 
The infusion should be stopped.
 
The patient should receive appropriate further treatment with an anti-histamine and/or acetaminophen if clinically indicated per the site's standard practice for management of IRR. Further medications can be administered if necessary.
 
Once symptoms have resolved or reduced to Grade 1, the infusion can be continued at a reduced (50%) infusion rate. If after one hour the patient's symptoms do not return and vital signs are stable, the infusion rate may be increased every 30 minutes, as tolerated, to the baseline rate.
 

Grade 3 Infusion-Related Reaction	
 
The infusion should be stopped promptly.
 
The patient must receive appropriate treatment with an anti-histamine and/or acetaminophen and/or methylprednisolone or equivalent and, if necessary, further medications (i.e., epinephrine, bronchodilator).
 
Only after the complete resolution to Grade <math>\leq 1</math>, and after having received appropriate prophylactic medication(s) as described above, the infusion may be resumed at an infusion rate of 25%. If after one hour the patient's symptoms do not return and vital signs are stable, the infusion rate may be increased to a maximum of 50%.
 
If after the resumption of infusion, symptoms return (irrespective of grade), the infusion must be stopped and the infusion tubing should be disconnected.
 
The duration of infusion may be prolonged in order to ameliorate IRR but TTI-621 dose does not require reduction.
 

Grade 4 Infusion-Related Reaction	
 
The infusion should be stopped promptly and the infusion tubing should be disconnected.
 
The patient should receive appropriate treatment with an anti-histamine and/or acetaminophen and/or methylprednisolone (or equivalent) and, if necessary, further medications (i.e., epinephrine, bronchodilator).
 
After discussion with the Sponsor Medical Monitor, the patient must not receive further infusions of TTI-621 if TTI-621 is judged by the Investigator to be the cause of the infusion-related reaction and the investigator feels that implementation of alternative or more aggressive prophylaxis would not be sufficient.
 

### 9.2.3.2. Hematologic Adverse Events Related to TTI-621 Administration

Blood counts should be monitored regularly as outlined in [Table 24](#), with additional testing obtained according to standard clinical practice. Management of hematologic adverse events associated with TTI-621 administration is summarized in [Table 13](#), [Table 22](#) and [Table 23](#). Platelet transfusion is allowed to manage severe thrombocytopenia to prevent and minimize bleeding according to ASH and ASCO guidelines. Per these guidelines, the platelet count threshold for prophylactic platelet transfusion is

$<10,000 \times 10^9/L$ . Investigators should consider the patient's medical history, concomitant medications and concurrent conditions to provide support for thrombocytopenia.

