#### 3.8.1. Expected Risks of TTI-621

In clinical trials to date enrolling almost 300 patients with a variety of oncologic indications across a range of TTI-621 dose levels primarily administered by intravenous infusion weekly until progression, TTI-621 has generally been safe and well-tolerated. In TTI-621-01, in which TTI-621 was administered intravenously on a weekly schedule in patients with various relapsed/refractory hematologic malignancies and select solid tumors, the most frequent treatment-related adverse event was infusion-related reaction in 44% of patients. The majority of infusion-related reactions were mild-to-moderate, with only 3% of patients experiencing infusion-related reactions Grade  $\geq 3$ . The infusion-related reactions were reported across all dose cohorts and occurred despite premedication with an anti-histamine and acetaminophen. This study incorporates a steroid into the prophylaxis regimen, which may be reduced or eliminated at the discretion of the Investigator in patients who do not experience infusion-related reaction.

The most frequent Grade  $\geq 3$  treatment-related adverse event was acute but reversible thrombocytopenia which occurred in 22% of patients and was not impacted by dose level. The transient decreases in platelet counts occurred in the 24 hours following infusion in the majority of subjects following intravenous exposure to TTI-621, consistent with augmented systemic phagocytic clearance of platelets. In the majority of cases, platelet counts returned to baseline levels within 1 week, enabling continued weekly dosing. No increased risk of bleeding or other clinical sequelae were observed. More detailed information about the known and expected risks and reasonably expected adverse events of TTI-621 may be found in the TTI-621 Investigator Brochure, which is the SRSD for this study.

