***Organ Function***

Adequate organ and hematologic function as defined below:

8. Serum aspartate aminotransferase (AST) and alanine aminotransferase (ALT)  $\leq$  3 x ULN;  $\leq$  5 x ULN in the presence of liver metastasis
9. Serum bilirubin (total)  $\leq$  1.5 x ULN ( $\leq$  2 x ULN if hyperbilirubinemia is due to Gilbert's syndrome)
10. Serum creatinine  $\leq$  1.5 x ULN OR creatinine clearance/estimated glomerular filtration rate (eGFR)  $\geq$  40 mL/min/1.73 m^2 if serum creatinine is  $>$  1.5 x ULN

11. Hemoglobin  $\geq$  9 g/dL; packed RBC transfusions are not allowed in the week preceding screening evaluation
12. ANC  $\geq 1.5 \times 10^9/L$
13. Platelet count  $\geq 100 \times 10^9/L$
14. INR  $\leq 1.5 \times$  ULN ( $\leq 2.5 \times$  ULN if on anti-coagulants) and PTT  $\leq$  5 seconds above the ULN unless receiving anti-coagulation therapy; patients on full-dose anti-coagulation must be on a stable dose of oral anti-coagulant or low molecular weight heparin, have therapeutic INR, no active bleeding (defined as within 14 days prior to first dose of study medication) and no pathological condition that carries a high risk of bleeding (e.g., tumor involving major vessels or known varices)
15. LVEF determined by echocardiogram or multigated acquisition scan  $> 50\%$

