**8.7.2. Concomitant Hematopoietic Growth Factors and Blood Products**

Myeloid growth factors are permitted for treatment-emergent Grade 3 or Grade 4 neutropenia. Likewise, erythropoiesis-stimulating or megakaryopoiesis-stimulating agents may be used for treatment-emergent anemia or thrombocytopenia, respectively. Transfusion thresholds for blood product support will be in accordance with institutional guidelines.

ASCO guidelines for use of WBC growth factors provide that 'prophylactic use of WBC growth factors for prevention of febrile neutropenia is warranted when the risk of febrile neutropenia is approximately 20% or higher and no other equally effective and safe regimen that does not require CSFs is available. Primary prophylaxis is recommended for the prevention of febrile neutropenia in patients who are at high risk on the basis of age, medical history, disease characteristics, and myelotoxicity of the chemotherapy regimen.' The NCCN guidelines for hematopoietic growth factors classify soft tissue sarcoma treated with doxorubicin as an example of disease setting and chemotherapy regimen with a high risk for febrile neutropenia (>20%) and recommends G-CSF prophylaxis for patients with high risk (>20%) of febrile neutropenia.

Thus, all patients receiving TTI-621 in combination with doxorubicin should receive prophylaxis with G-CSFs for prevention of febrile neutropenia associated with doxorubicin. Suggested prophylaxis is pegfilgrastim and discussion with the Sponsor Medical Monitor regarding the specific agent is encouraged.

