**Table 13. Management of Hematologic Adverse Events Associated with TTI-621 Administration**

Note that specific guidelines for management of thrombocytopenia regardless of attribution to TTI-621 and/or doxorubicin are provided in [Table 22](#) and [Table 23](#) and are not described here.

Observation	Management Guidelines
Grade 4 neutropenia lasting > 72 hours	
 
Delay TTI-621 dosing until the re-treatment criterion (ANC <math>> 1.0 \times 10^9/L</math>) is met, then resume TTI-621: 
 
At the same dose if dose delay was <math>\leq 1</math> week
 
One dose level reduction if dose delay was <math>> 1</math> week
 
One dose level reduction if the event recurs
 
 
 

Grade 3 febrile neutropenia lasting > 72 hours Grade 3 neutropenia with clinical evidence of infection Grade 4 febrile neutropenia	
 
Delay TTI-621 dosing until the re-treatment criterion (ANC <math>> 1.0 \times 10^9/L</math>) is met, then resume TTI-621 at one dose level reduction
 

Grade 3 anemia	
 
Delay TTI-621 dosing until resolution to Grade <math>\leq 1</math> or baseline, then resume TTI-621 treatment: 
 
At the same dose if dose delay was <math>\leq 1</math> week
 
One dose level reduction if dose delay was <math>> 1</math> week
 
One dose level reduction if the event recurs
 
 
 

Grade 4 anemia	
 
For Grade 4 events, discontinuation of TTI-621 should be considered. If, per Investigator's assessment, it is in the patient's best interest to continue the treatment, TTI-621 treatment can be resumed when the AE resolves to a level that meets re-treatment criteria
 

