$50 \times 10^9 – 25 \times 10^9/L$	
 
Omit TTI-621 on Day 8
 
Monitor platelet recovery (CBC twice weekly recommended)
 
Consider platelet transfusion per ASCO guidelines if clinically indicated
 
On Day 1 of next cycle: 
 
if platelets have recovered to <math>\geq 75 \times 10^9/L</math>, initiate cycle with doxorubicin at the same dose and TTI-621 at one dose level reduction
 
if platelets have not recovered to <math>\geq 75 \times 10^9/L</math>, hold doxorubicin and TTI-621 and monitor platelets; initiate the cycle when platelets recover to <math>\geq 75 \times 10^9/L</math> with doxorubicin at same dose and TTI-621 at one dose level reduction
 
 
 
In the case of a second occurrence of platelet count decrease to <math><50 \times 10^9</math>, follow the guidelines above or consult with the Sponsor Medical Monitor regarding management
 
The reduced dose of TTI-621 should be used for the remaining combination cycles
 
When the subject completes the combination portion of the study and moves to TTI-621 monotherapy: 
 
the original TTI-621 dose level should be re-instated and platelet counts monitored
 
in the case of platelets <math>< 50 \times 10^9/L</math> without other causality on Day 15, hold TTI-621 until platelets are <math>\geq 50 \times 10^9/L</math> and then continue with TTI-621 at a one dose level reduction
 
on second occurrence of platelets <math>< 50 \times 10^9/L</math> without other causality, reduce TTI-621 by an additional dose level and monitor for tolerability or consult with the sponsor medical monitor regarding management
 
in the absence of disease progression, further dose reductions may be implemented after discussion with the sponsor medical monitor
 
 
 

Platelet Count on Day 8	Management Guidelines

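### Protocol Section 9.2.3.2 prints the prophylactic platelet transfusion threshold as <10,000 × 10⁹/L, 100 to 400 times the protocol's other visible numeric platelet cut-offs; probably a per-microlitre number with a per-litre unit.

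*Protocol*

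**What the plan says.** Protocol Section 9.2.3.2 covers hematologic adverse events related to TTI-621. It states: "Platelet transfusion is allowed to manage severe thrombocytopenia to prevent and minimize bleeding according to ASH and ASCO guidelines". The next sentence reads "Per these guidelines, the platelet count threshold for prophylactic platelet transfusion is" and ends, across a page break, with <10,000 × 10⁹/L.

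Three other places bear on transfusion, and none gives a number:

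- Section 8.7.2: "Transfusion thresholds for blood product support will be in accordance with institutional guidelines".
- The note to Table 13, in the same subsection as the printed figure, sends platelet management elsewhere: "Note that specific guidelines for management of thrombocytopenia regardless of attribution to TTI-621 and/or doxorubicin are provided in" Tables 22 and 23.
- Tables 22 and 23 (Section 9.5), in the rows below 50 × 10⁹/L: "Consider platelet transfusion per ASCO guidelines if clinically indicated".

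The visible numeric platelet cut-offs elsewhere are all on the 10⁹/L scale: 100 for entry (Section 6.2, criterion 13), 75 to start a new TTI-621 cycle or re-treat with doxorubicin (Tables 9 and 16), and 75, 50 and 25 in Tables 22 and 23.

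**The concern.** The printed threshold is on a different order of magnitude from every numeric platelet cut-off it can be compared with. Read literally, it would make a patient who only just meets the entry criterion eligible for prophylactic transfusion, which contradicts the restriction to severe thrombocytopenia in the sentence before it.

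The toxicity is an important one here. For the earlier intravenous study, Section 3.8.1 says the most frequent Grade ≥3 "treatment-related adverse event was acute but reversible thrombocytopenia which occurred in 22% of patients". Thrombocytopenia and hemorrhage are both adverse events of special interest (Section 13.5.8). SAP Section 4.3.2 records that Grade 3 or 4 thrombocytopenia on Day 8 at 2 mg/kg led to Cohort B enrollment being stopped after 18 patients. This is the only numeric transfusion threshold visible in the protocol, and as printed it cannot work as a trigger.

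**Working it through.** The check needs only a unit conversion (1 L = 10⁶ µL) and ratios. The protocol makes no calculation of its own here, so there is none to reproduce; the stated figure is taken as printed.

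**Step 1. Convert the printed figure.**

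10,000 × 10⁹/L = 10¹³/L; 10¹³ ÷ 10⁶ = 10⁷/µL = 10,000,000/µL.

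**Step 2. Compare it with the visible numeric cut-offs.** Ratio = 10,000 ÷ cut-off, both in 10⁹/L.

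| Cut-off (× 10⁹/L) | Where | Ratio |
|---|---|---|
| 100 | Inclusion criterion 13 | 10,000/100 = 100 |
| 75 | Tables 9, 16, 22, 23 | 10,000/75 = 133.3 |
| 50 | Tables 22, 23 | 10,000/50 = 200 |
| 25 | Tables 22, 23 | 10,000/25 = 400 |

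The rows of Tables 22 and 23 that start at the lower limit of normal give no number for that limit, and the dose-limiting toxicity criteria in Section 5.4 are redacted. Neither is used.

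**Step 3. Place a patient at the entry minimum.**

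100 ÷ 10,000 = 0.01. A patient with the lowest count allowed at entry is at 1% of the printed trigger, and so meets it.

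**Step 4. Test the likely explanation (assumption: the number was meant per microlitre).**

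10,000/µL × 10⁶ µL/L = 10¹⁰/L = 10 × 10⁹/L.

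- Against the printed value: 10,000 ÷ 10 = 1,000 times lower.
- Against the lowest management cut-off: 10 ÷ 25 = 0.4.

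A threshold of 10 × 10⁹/L falls inside the <25 × 10⁹/L row of both tables and is consistent with severe thrombocytopenia. The printed value fits none of the low-count rows.

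**The case against.** The strongest reply is that the error does little harm.

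- **Other text governs practice.** Platelet-driven dosing runs through Tables 9, 16, 22 and 23, all of which are plausible. Transfusion thresholds are left to institutions by Section 8.7.2, and Tables 22 and 23 point to ASCO. Without bleeding, those tables raise transfusion only below 50 × 10⁹/L. The faulty sentence reports what guidelines say, and the section asks investigators to weigh the individual patient.
- **The slip is obvious.** A threshold that every patient meets is more likely to be recognised as a unit error than followed. A wrong but plausible number would be more dangerous.
- **Bleeding was not a problem before.** Section 3.8.1 reports: "No increased risk of bleeding or other clinical sequelae were observed".
- **The figure might be a misread exponent, or already corrected.** 10,000 × 10⁶/L would also equal 10 × 10⁹/L. SAP Section 4.3.2 cites a PACL No 5 aimed at thrombocytopenia, and the numbering suggests earlier letters that are not in the file. It also describes the Cohort C patients as already enrolled, which limits the benefit of a change now.
- **The replacement value is not verified**, because the cited guidelines are not part of the documents.

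The first two points stand and limit the severity. The third stands only in part: that study's combination partners were rituximab and nivolumab (Section 3.5.2.1), so it says nothing about bleeding when doxorubicin is added. The fourth is speculation. Nothing in the documents shows a misreading or a correction, and the misread-exponent route leads to the same intended value of 10 × 10⁹/L. The last point is right, which is why the correction is conditional on a check.

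**Conclusion.** The concern holds. The printed threshold is wrong as written: it is 100 times the entry minimum and 400 times the lowest management cut-off, and it contradicts the severity condition in the sentence before it. Those ratios rest only on numbers visible in the protocol.

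That the intended value is 10 × 10⁹/L, and hence that the printed figure is 1,000 times too high, rests on the assumption that the number was meant per microlitre. The arithmetic fits well, but confirmation has to come from the cited guidelines.

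The practical consequence is small, and the sample size and data are unaffected. It should be corrected nonetheless: it is a decision threshold in an operative safety section, for a toxicity that closed a cohort, and no other visible text states the right number.

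**What to change.** In Section 9.2.3.2, replace the figure with <10 × 10⁹/L (10,000/µL), after checking it against the ASH and ASCO guidelines the section cites. Giving both units removes the ambiguity. If an earlier administrative letter has already made the change, cite it and carry the correction into the next protocol version.

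The cost is one figure in a clarification letter, with no change to design, analysis or data collection.
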